## **INTRODUCTION**

### **Background and rationale**

The first-line treatment for idiopathic nephrotic syndrome in children is oral corticosteroids.[1] Most children experience several relapses of nephrotic syndrome, needing repeated courses of corticosteroid therapy or even more aggressive treatment with other immunosuppressive drugs. For most children, long-term prognosis is for complete resolution of their disease over time with maintenance of normal kidney function. Therefore, it is vital to focus on minimizing adverse events of the disease and its treatment. The aim of the RESTERN study (REducing STERoids in Relapsing Nephrotic syndrome) is to assess the safety and effectiveness of a reduced alternate day steroid schedule for treatment of a nephrotic syndrome relapse in comparison with the current standard therapy.

### **Objectives**

Primary objective

To study the effectiveness of a reduced corticosteroid schedule for the treatment of a relapse in children with steroid sensitive nephrotic syndrome.

Secondary objectives

- To study the influence of maintenance immunosuppressive therapy on the effectiveness of a reduced steroid schedule for the treatment of a relapse in children with steroid sensitive nephrotic syndrome. Maintenance immunosuppressive therapies include levamisole, cyclosporine, tacrolimus, mycophenolate mofetil and mycophenolate sodium, and alternate day prednisolone with a maximum of 4 mg/m^2;
- To investigate the occurrence of relapses, frequency of relapses and progression to steroid dependent and frequent relapsing nephrotic syndrome in children with nephrotic syndrome under the standard treatment regimen;
- To study the influence of maintenance immunosuppressive therapy on the occurrence of subsequent relapses, frequency of subsequent relapses and progression to steroid dependent and frequent relapsing nephrotic syndrome under the standard regimen, and;
- To study the effectiveness of a reduced steroid schedule for the treatment of a relapse and occurrence and frequency of subsequent relapses in children with steroid dependent nephrotic syndrome.

## **STUDY METHODS**

### **Trial design**

National, single center, double-blind, randomised, placebo controlled, noninferiority intervention study.

### **Randomisation**

After prednisolone 60 mg/m^2 daily in 1 dose until complete remission for 3 days, randomisation (allocation ratio 1:1) between:

- Standard treatment: 6 weeks prednisolone 40 mg/m^2 (max. 40 mg) every other day;

- Study treatment: 2 weeks prednisolone 40 mg/m^2 (max. 40 mg) every other day, then 4 weeks placebo every other day.

### **Blinding**

All researchers involved in the preparation of the analysis plan don't have access to trial data broken down by treatment allocation. Once data quality checks are satisfactory and the database is locked, a blind review will be undertaken to quantify missing data of the entire dataset and allow for any final amendments to the statistical analysis plan. During interim analysis and interpretation, group allocation will be masked using dummy group names (for example, group A, group B). The true group allocation will be unmasked only if necessary and after the database is locked. In addition, due to a difference of 4 weeks between the standard treatment and placebo group regarding timing of final prednisolone dose, time to first relapse and thereby all final statistical analyses can only be determined after unblinding. The randomisation list remains preserved by the hospital trial pharmacy and will not be accessible to the investigators until the end of the follow-up of the last patient. An unblinding procedure at the hospital pharmacy department will be available at all times.

### **Sample size**

From previous studies, we know the incidence of nephrotic syndrome in Dutch children to be 1.52/100,000 children/year.[2] Eighty percent of the pediatric patients develop at least 1 relapse of whom 50% continue towards frequent relapsing nephrotic syndrome. Based on data from previous studies, average time to relapse in the first year is approximately 185 days (standard deviation of 120 days).[3] Using the power calculation for a noninferiority trial with a continuous primary outcome, a power of 80% and a noninferiority limit of 50 days, 72 patients per group are required. Using a Cox Proportional Hazard time-to-relapse analysis (survival analysis)[4], similar numbers can be calculated.

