### **Analysis methods**

#### Primary endpoint

##### Time to first relapse after the final prednisolone dose

- As normal distribution is not assumed, the median time to relapse will be compared between the groups using a Mann-Whitney test;
- In case patients did not experience any relapse after 24 months or patients are lost to follow up before they experienced a relapse, incidence rates or person-time rates will be used to compare the groups;
- If a normal distribution is shown in the Shapiro-Wilk W test, a *t* test will be used;
- The percentages of study subjects with a relapse at 12 and 24 months will be compared between the groups;
- The cumulative probability on the absence of a relapse will be estimated by survival analysis, according to the Kaplan-Meier method. Log-rank tests are used for the comparison between the standard treatment group and placebo group;
- To test for the influence of factors, such as the use of maintenance immunosuppressive therapy, logistic regression analysis for nephrotic syndrome relapses with covariate analysis will be performed;
- Within each subject time to relapse after study medication will be compared to time to relapse before entering the study using a paired sample *t* test. This test will exclusively be performed in patients without changes in maintenance therapy.

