### **Interim analysis**

The total inclusion of 144 patients is expected to be finalized in 1.5 years, thereby the DSMB meeting will take place approximately 8 months after the start of inclusion. The mean follow-up period of the 40 patients at that time will be 5.5 (range 3-8) months. Previous literature shows a cumulative incidence rate of a first relapse of 30% after 5.5 months.[3] As the placebo group will receive approximately 35% less prednisolone during the study period, we based the power calculation on a difference of maximum 1/3rd earlier until the first relapse after study medication. Therefore we would like to advise the DSMB to check whether the patients with a relapse are in group A or B (dummy groups) if over 8 patients have experienced a relapse at interim analysis. Aim is then to check for a significant difference in relapse rate between the two groups. If there seems to be a significant difference between the two groups and the percentage of patients with a relapse in either one or both groups exceeds 40% than they might consider to unblind the groups.

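### The sample size gives every child an observed relapse time, so the stated 80% power is overstated, and the Cox cross-check does not hold at the margins the SAP's figures suggest

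*SAP*

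**What the plan says.** - **SAP, Sample size.** The inputs come from previous studies: "average time to relapse in the first year is approximately 185 days (standard deviation of 120 days"). The method is given as "Using the power calculation for a noninferiority trial with a continuous primary outcome", and the result is "a power of 80% and a noninferiority limit of 50 days, 72 patients per group are required". No alpha is given, and there is no term for censoring, for children who do not relapse, or for dropout. The section adds that a Cox-based calculation leads to much the same size, without a hazard ratio or an event count. It also says of the disease in general: "Eighty percent of the pediatric patients develop at least 1 relapse".
- **SAP, Outcome definitions, Primary outcome.** Time to first relapse runs in days from the last prednisolone dose, with censoring at 12 and at 24 months.
- **SAP, Analysis methods, Primary endpoint.** Days are compared by Mann-Whitney or *t* test, alongside Kaplan-Meier and log-rank. Person-time rates are the provision for this case: "In case patients did not experience any relapse after 24 months or patients are lost to follow up before they experienced a relapse".
- **SAP, Interim analysis.** The reference that supplies the 185 days is cited for a "cumulative incidence rate of a first relapse of 30% after 5.5 months". Total inclusion is 144, which is exactly twice 72.
- **SAP, Level of confidence intervals and p-values.** Non-inferiority is decided from a two-sided 95% confidence interval.

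**The concern.** The formula treats the outcome as a fully measured number of days in all 144 children. The rest of the SAP treats it as a censored event time that some children will not reach. The two figures taken from the same reference also pull apart. A mean of 185 days with SD 120 over all children suggests that nearly all relapse within a year, while 30% at 5.5 months suggests a much slower process.

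If a substantial share of children do not relapse, the information in the trial is less than the formula counts. An inconclusive result would then be read against a power of 80% that the design did not have.

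**Working it through.** **1. The SAP's own figure.** Inputs from Sample size: margin 50 days, SD 120, power 80%, true difference taken as 0.

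n = 2 × (120/50)² × (z_α + z_β)²

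- One-sided 5%: 2 × 5.76 × (1.645 + 0.842)² = 71.2, so 72. This reproduces. Power at 72 is Φ(50/(120√(2/72)) − 1.645) = Φ(2.50 − 1.645) = 80.4%.
- One-sided 2.5%: 91 per group. This does not reproduce; power at 72 is 70.5%.

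The 72 therefore rests on one-sided 5% and on 72 usable times per group.

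**2. Do 185/120 and the 30% fit together?** 5.5 months is 167 days.

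| Shape with mean 185, SD 120 | Relapsed by day 167 | By day 125 |
|---|---|---|
| Normal | 44% | 31% |
| Beta on 0–365 days | 46% | 37% |
| Weibull | 51% | 37% |
| Gamma | 53% | 37% |
| Lognormal | 55% | 36% |

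Day 125 is 167 minus the 42 days of standard treatment. It applies if the 5.5 months run from inclusion rather than from the last dose. On a common clock the fit is poor; on the shifted clock it is nearly acceptable.

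**3. What the 30% implies.** Assumption: constant hazard.

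- λ = −ln(0.70)/167.4 = 0.00213 per day.
- Relapsed by 12 months: 1 − exp(−365λ) = 54%, about 39 per group.
- Relapsed by 24 months: 1 − exp(−730λ) = 79%, about 57 per group or 114 in all.
- Time restricted to 12 months, all children: mean 254 days, SD 128.

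**4. Power with 72 randomised per group.** Means: Φ(50/(SD√(2/m)) − z_α), with m children per group in the comparison. Time to event: Φ(ln(HR)√d/2 − z_α), with d events. The hazard-ratio margins are assumptions. 1.37 is 185/135, the 50-day margin read as a ratio of means. 1.5 is 1/(1 − 1/3), from the one-third earlier relapse described under Interim analysis.

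| Analysis | One-sided 5% | One-sided 2.5% |
|---|---|---|
| As planned, 72 times per group, SD 120 | 80% | 71% |
| All children, restricted to 12 months, SD 128 | 76% | 65% |
| Relapsers only, 57 per group | 72% | 60% |
| Relapsers only, 39 per group | 58% | 45% |
| Time to event, 114–115 events, HR 1.5 | 70% | 58–59% |
| Time to event, 114–115 events, HR 1.37 | 51–52% | 39% |

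114 events correspond to 79% relapsing, 115 to 80%. Stopping the time-to-event analysis at 12 months (about 78 events) would lower the last two rows to 56% and 40% at one-sided 5%.

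**5. The Cox cross-check.** Events needed for 80% power at one-sided 5%: d = 4(1.645 + 0.842)²/(ln HR)².

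- HR 1.5: 151 events.
- HR 1.37: 250 events.

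Both exceed 144. If every child relapsed, HR 1.5 would give 78.5%. With 114 events, 80% power needs ln HR = 2 × 2.487/√114 = 0.466, a margin of about 1.59. The SAP states no such margin.

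**The case against.** **The two figures are not strictly incompatible.** A reader might infer that 185/120 cannot describe all children. That is not proven. On 0–365 days, a mean of 185 and SD of 120 allow anything from 18% to 75% relapsed by day 167. The 30% has no stated time origin, and a shift of six weeks brings the normal shape to 31%. This stands.

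**185/120 need not be a relapsers-only figure.** This second inference is also tempting. The constant-hazard model gives first-year relapsers a mean of 159 days (SD 104), not 185 (120). A 12-month mean over all children, with non-relapsers counted at 365 days, comes nearer: a restricted mean of 185 goes with SD 128. That reading implies 51% relapsed by day 167 (41% by day 125), so it does not recover the 30%. Taken at face value with SD 120, it would preserve 80% at one-sided 5%, but only for a 12-month restricted-time comparison, which the SAP neither describes nor plans. Only the cited study can settle whom 185/120 covers.

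**Non-relapsers are not discarded.** Kaplan-Meier, log-rank and person-time rates use all 144 children, and the SAP nowhere says that children without a relapse leave the Mann-Whitney comparison. The 39 and 57 per group are therefore one scenario, not the plan's stated analysis. This stands, and it is why the loss is a range.

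**The 80% who ever relapse is only a guide.** It describes paediatric patients generally, whereas the trial enrols children already in a relapse.

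**Alpha is a separate matter.** The fall from 80% to 71% with all 72 times observed comes from the two-sided 95% interval and should not be attributed to non-relapse.

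**Conclusion.** The point holds in a limited form. The 72 per group gives 80% power at one-sided 5% when every child supplies a time with SD 120. The SAP itself foresees children without a relapse and makes no allowance for them, so the 80% is overstated. Under a constant hazard through 30% at 5.5 months, with observation to 24 months for the event analyses, power at one-sided 5% is roughly 52–76%. Where it falls depends on the analysis and on a hazard-ratio margin that the SAP does not give. At the one-sided 2.5% that the SAP's interval implies, the same analyses give roughly 39–65%; part of that further fall is the alpha issue alone.

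The Cox statement does not hold at either margin suggested by the SAP's own figures. It comes close only at 1.5 with every child relapsing, or with an unstated margin near 1.6.

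The documents do not establish that 185/120 is impossible for all children, nor that it describes relapsers only.

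**What to change.** In the SAP's Sample size section:

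1. State which children the 185 days (SD 120) describes and how those without a relapse were counted. Take this from the cited study; do not assert that it means relapsers only.
2. State the time origin of the 30% at 5.5 months (inclusion, or last prednisolone dose), here and under Interim analysis.
3. Replace the 80% with the power for time to first relapse in all 144 children. Give the expected event fraction at the analysis time, the hazard-ratio margin with its derivation from 50 days or from one third, and the alpha that matches the two-sided 95% interval.
4. Supply the inputs to the Cox calculation and correct its result, or remove the sentence.

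The cost is a recalculation, some rewording and a less favourable stated power. No extra patients are required.

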## **STATISTICAL PRINCIPLES**

### **Level of confidence intervals and p-values**

For this noninferiority trial, the upper bound of the 2-sided 95% confidence interval for the treatment effect has to be below the margin to declare that noninferiority has been shown. P-values <0.05 will be considered statistically significant.

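### The 72 per group match 80% power only at a one-sided 5% level; under the SAP's two-sided 95% confidence interval rule the same calculation gives about 70%

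*SAP*

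**What the plan says.** The Sample size section of the SAP takes from earlier studies that "average time to relapse in the first year is approximately 185 days (standard deviation of 120 days"). It then describes the method, "Using the power calculation for a noninferiority trial with a continuous primary outcome", and concludes that for "a power of 80% and a noninferiority limit of 50 days, 72 patients per group are required". No significance level or sidedness appears in that section. It adds that with a Cox model "similar numbers can be calculated", without a hazard ratio margin, an event rate or a level.

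The section on the level of confidence intervals and p-values sets the decision rule: "the upper bound of the 2-sided 95% confidence interval for the treatment effect has to be below the margin".

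The Interim analysis section confirms the total: "The total inclusion of 144 patients is expected to be finalized in 1.5 years". The same section says "we based the power calculation on a difference of maximum" one third earlier first relapse after study medication.

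**The concern.** A noninferiority decision on the bound of a two-sided 95% interval is a one-sided test at 2.5%. A sample size claimed to give 80% power should give it at that level. If the size was computed at one-sided 5% (a two-sided 90% interval), the trial is less likely to succeed than the plan says. A reduced schedule that is truly no worse would then miss the margin more often than the stated one time in five. Readers of an inconclusive result would misjudge how likely that was by design. There would also be a temptation to move to a 90% interval afterwards.

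**Working it through.** **Inputs**
- Standard deviation 120 days, mean 185 days, limit 50 days, power 80%, 72 per group: Sample size section.
- Total 144, which agrees with 2 × 72: Interim analysis section.
- Allocation 1:1: Randomisation section.
- Decision level one-sided 2.5%: implied by the two-sided 95% interval.
- True difference 0 and no dropout: my assumptions; the SAP states neither.

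**Reproducing the plan's figure**

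n per group = 2 × (z_α + z_β)² × SD² / margin², with 2 × 120² / 50² = 11.52 and z_β = 0.842.

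- One-sided 5%: 11.52 × (1.645 + 0.842)² = 71.2, so 72. This is the plan's figure.
- One-sided 2.5%: 11.52 × (1.960 + 0.842)² = 90.4, so 91 (92 by the noncentral t distribution). This is not the plan's figure.

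**Power with 72 per group**

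Standard error = 120 × √(2/72) = 20 days, so margin / SE = 50 / 20 = 2.5.

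| Level | Power, normal | Power, noncentral t |
|---|---|---|
| One-sided 5% | Φ(2.5 − 1.645) = 80.4% | 80.0% |
| One-sided 2.5% | Φ(2.5 − 1.960) = 70.5% | 70.0% |

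Turned round, 72 per group is also what the formula returns for 70% power at one-sided 2.5%.

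**Could other inputs rescue 72 at one-sided 2.5% and 80% power?** The margin would have to be 20 × (1.960 + 0.842) = 56 days, or the standard deviation 50 × √(72/2) / 2.802 = 107 days. The SAP gives neither. A dropout allowance or a small-sample correction only raises the number, and so does a true disadvantage of the reduced schedule.

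**The one-third difference.** 185 / 3 = 61.7 days, against 50 / 185 = 27%. With 61.7 days in the same formula, n is 47 per group at one-sided 5% and 60 at one-sided 2.5%. Neither is 72, so the calculation of means did not use one third of 185 days.

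**The Cox remark.** With its inputs missing, only assumed cases can be tried. Events = 4 × (z_α + z_β)² / ln(HR)².

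| Assumed hazard ratio margin | One-sided 5% | One-sided 2.5% |
|---|---|---|
| 1.5 (one third earlier, exponential times) | 151 | 191 |
| 185/135 = 1.37 (50 days earlier, exponential times) | 250 | 317 |

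The answer depends wholly on the assumed margin and level. One of the four cases comes near 144, and then only if almost every child relapses.

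**The case against.** The best defence is that the Sample size section names no level, and that the protocol, which is not at hand, may do so. That does not remove the problem. The point is not that a level is missing, but that the power claim and the decision rule in this one document do not agree. A one-sided 5% level in the protocol would itself conflict with the SAP's interval rule. Nothing in the SAP mentions one-sided 5% or a 90% interval.

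A second objection stands as a limit on the claim. The Analysis methods section makes the Mann-Whitney test the default, adds Kaplan-Meier and log-rank, and reserves the *t* test for normally distributed data. A reader might infer that the trial's primary analysis has 70% power. The documents do not support that: 70% is the power of the mean-difference calculation that the SAP presents.

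Two stronger readings are also tempting.

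- *That there are two rival margins, so a bound between 50 and 62 days could be read either way.* Only the Sample size section names a noninferiority limit, and it is 50 days. The one-third statement sits in advice to the DSMB, gives no number of days and is not called a margin. It may describe the Cox calculation. It needs reconciling, but the SAP does not show which of the two statements is the slip.
- *That the Cox remark is false.* It cannot be checked. A hazard ratio of 1.5 at one-sided 5% needs 151 events, which could fairly be called similar to 144. A power figure for the Cox analysis would also need one consistent event model, and the SAP's figures do not supply it. An exponential mean of 185 days implies about 59% relapsed at 5.5 months, while the Interim analysis section cites 30%, which implies a mean of about 469 days.

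**Conclusion.** The point holds for the calculation of means. The 72 per group reproduce at 80% power only at one-sided 5%. Under the SAP's two-sided 95% interval, 91 per group are needed (92 by noncentral t), and 72 per group give about 70%. The chance that a truly equivalent schedule fails is therefore about 30% rather than 20%. This rests on a standard deviation of 120 days, a margin of 50 days, a true difference of 0 and no dropout; losses or a true disadvantage would lower the power further. The type I error of the decision rule is unaffected and stays at one-sided 2.5%.

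The one-third statement does not match 50 of 185 days and should be clarified. The Cox remark is unsupported as written. Neither goes further than that.

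**What to change.** Keep 144 patients and the two-sided 95% interval.

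- **Sample size section:** state the level (one-sided 2.5%) and restate the power as about 70% for 72 per group, standard deviation 120 days and limit 50 days, for a comparison of means with zero true difference and no dropout.
- **Interim analysis section:** reconcile the one-third difference with the 50 days, say which one the power calculation used, and state that 50 days is the only noninferiority limit.
- **Cox sentence:** give its hazard ratio margin, expected event rate and result at one-sided 2.5%, or delete it.

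The cost is SAP wording and a less favourable power figure, with no extra patients. The Blinding section already allows final amendments to the SAP at the blind review. If the sponsor wants to keep 80% power and recruitment allows it, the alternative is 91 to 92 per group (182 to 184 in total, 38 to 40 more) before any dropout allowance. Moving to a two-sided 90% interval would also reproduce 72, but it doubles the one-sided error from 2.5% to 5% and would need explicit prespecification and justification.

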### **Timing of interim analysis and stopping guidance**

Interim analysis will be performed by the Data Safety and Monitoring Board (DSMB), three months after inclusion of the first 40 participants. The study will be terminated in a premature stage if the safety of participants is jeopardized. As the placebo group only receives less active medication (in comparison with the standard treatment group), the occurrence of any serious adverse event is considered highly unlikely. The only risk may be found in the primary outcome of the study, i.e. significant inferiority of the placebo-treatment schedule with regards to time to next nephrotic syndrome relapse.

### **Timing of final analysis**

Final analysis will take place after completion of the 24 months follow-up period of the last study subject.

